**Power Analysis:** The lack of prior RCTs of mobile interventions in BD or SZ makes it challenging to determine the effect size with which to power the study. The underlying assumption of our RCT is that effect sizes will be comparable to that seen in in-person CBT; Accordingly, we conservatively powered the study based results of recent meta-analyses of CBT in SZ and BD in a total of 46 RCTs, which revealed a median effect size of 0.4 (small to moderate) in favor of CBT with active comparators. Sample size estimates were based on the Hedeker, et al. method for various covariance structures for mixed effects models. For the proposed study, we assumed an autoregressive covariance structure, with conservative correlation between sequential assessments set at 0.5. Using this methodology, assuming an alpha level of 0.05, we have a minimum 80% power to detect a medium effect size with 20% attrition at 12 weeks (based on pilot data) when there are 85 subjects per each condition for a total of 255 subjects.

**Hypothesis 2 (Secondary Outcomes):** Compared to EMA-only and Standard Care, the CBT2go intervention will be associated with greater improvement in EMA and standard lab-based measures of medication adherence, social functioning, and hospitalization and emergency service utilization. **Dependent Variables:** EMA-outcomes; Medication adherence Composite; SFS Score; PSR Toolkit Composite and Hospitalizations/ER visits. **Independent Variables:** Condition and Time (0,6,12,24 Weeks).

**Statistical Analysis:** As above, this hypothesis will be tested using GAMMs. Condition will be entered into the model as a fixed-effect predictor along with time on study and their interaction, and we will test for all pairwise differences (e.g., CBT2go vs. Standard Care) with Westfall-Young adjusted p values. EMA outcomes (which include up to 252 observations per person) will be assessed with Hierarchical GLM analyses with a multinomial sampling model with a logit link functioning, with time (days in study) as a predictor and Condition (CBT2go vs. EMA-only) as a predictor of intercept and growth parameters of the model.

**Power Analysis:** Our secondary outcomes have the same assumptions as those in Hypothesis 1 and thus are independently powered to detect a medium effect size for each measure. The power to detect differences by condition with EMA analyses should be equal or greater by virtue of number of observations.

**Hypotheses 3 and 4 (Moderators and Mediators):** Neurocognitive ability will account for more variation in device compliance and treatment response than diagnostic group; Improvement in cognitive insight and reduction in dysfunctional beliefs will mediate treatment response. **Dependent Variable:** Outcome (Slope of change in BPRS between Baseline and Week 24) **Independent Variables:** **Moderators:** Cognitive ability (MCCB); Diagnosis (BD vs. SZ); **Mediators:** Insight (BCIS) and Dysfunctional Attitudes (DAS).

**Statistical Analysis:** The primary moderation and mediation analysis will be based on the recommendations of Kraemer et al. MacArthur Network. Moderation (Diagnosis, MCCB) will be confirmed by the presence of a significant interaction effect (Diagnosis x Condition) on trajectories using GAMMs, and that the diagnosis interaction effect will no longer attain significance with cognitive ability entered into the model. For mediation, we will assess for: (1) non-zero relationship between the mediator and Condition and (2) non-zero relationship between the mediator and outcome. We will implement the test for mediation by (1) fitting mixed models testing for treatment differences in BCIS and DAS trajectories by week 6; (2) fitting mixed models testing for BCIS and DAS differences in trajectories of BPRS from week 6 to 12; (3) testing whether the product of coefficients from these two models assessing change in mediators and outcomes is significantly different from zero using the bootstrap test of Preacher et al. (2004).

**Power Analysis:** Based on the Fritz and McKinnon's estimates for sample size to detect mediation, and conservatively using change scores to compute power, we have at least 80% power to detect mediation with the hypothesized effect size.

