**EMA Measures of Symptoms, Medication Adherence, and Socialization (Secondary Outcome):** EMA ratings are single-item, thrice daily 1-7 scales (1 “not at all” to 7 “extremely”) for severity of depression, voices, and mania, along with medication adherence (binary yes or no response) and socialization (number of social interactions).

**Beck Anxiety Inventory (Secondary Outcome):** The BAI is a 21-item self-report inventory rated on a scale from 0 to 3. This will allow us to determine how the subject has been feeling in the last month in terms of severity of anxiety. Each item is related to subjective, somatic, or panic-related symptoms of anxiety and the responses range from “not at all” to “severely”

**Medication Adherence (Secondary Outcome): Self-report:** The Medication Adherence Rating Scale will be used, which asks about the willingness and ability to take your medications every day. It has been used to measure medication adherence in psychosis

**Social Functioning Scale (Secondary Outcome):** We will assess social function with the Birchwood Social Functioning Scale (SFS), a 79-item self-report of social functioning across 7 domains: 1) social engagement, 2) interpersonal behavior, 3) prosocial activities, 4) recreation, 5) independence/competence, 6) independence/performance, and 7) employment. The SFS is

administered in interview (versus self-report) and best estimate ratings are based on observations

**Specific Levels of Functioning Scale (Secondary Outcome):** The SLOF is a multidimensional behavioral survey administered to the caseworker or caregiver of a patient with schizophrenia. The scale assesses the patient's current functioning and behavior across six different domains. We will be looking at only 4 of them: Interpersonal Relationships, Social Acceptability, Activities of Community Living, and Work Skills. Each of these questions is rated on a 5-point Likert scale. The lower the total score means the better overall functioning of the patient.

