**EMA Questions:** Participants will respond to surveys three times per day for 12 weeks. The frequency (3 times per day, morning, mid-day, evening) and timing (random initiation at approximately 2 hour intervals) of EMA surveys are based on preliminary data described above. In each of morning, mid-day, and evening surveys, participants will be prompted to answer multiple-choice questions (i.e., they do NOT type in answers) asking: What are you doing? (e.g., working, non-physical leisure), Who are you with? (e.g., alone, with family), Where are you? (e.g., at home, at work), and 7-point Likert scales are used to rate mood and symptoms (e.g., Are you sad? “Not at all” to “Extremely” or Have you been bothered by voices? “No voices” to “Extremely”). They also report whether or not they have taken prescribed medications and the number of social interactions since the last signal. The format of these questions is identical between EMA-only and CBT2go.

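### The SAP fits all EMA outcomes with one multinomial logit and names no ordinal form for the 1-7 symptom ratings, so the usual reading gives no single signed treatment effect

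*SAP*

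**What the plan says.** The SAP's dependent variables for Hypothesis 2 are "EMA-outcomes; Medication adherence Composite; SFS Score; PSR Toolkit Composite and Hospitalizations/ER visits". The lab-based outcomes go to GAMMs. All EMA outcomes go to a single specification, "Hierarchical GLM analyses with a multinomial sampling model with a logit link functioning". In that model the day of study is a covariate, and the arm, CBT2go or EMA-only, acts on both the starting level and the rate of change. The SAP does not say whether the logit is cumulative, adjacent-category or baseline-category. It names no reference category and no check of proportional odds.

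Protocol section 9 describes three kinds of EMA variable under the title "EMA Measures of Symptoms, Medication Adherence, and Socialization (Secondary Outcome":

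- Symptom severity (depression, voices, mania): "EMA ratings are single-item, thrice daily 1-7 scales", anchored from not at all to extremely.
- Medication adherence: a yes/no answer.
- Social contact: "socialization (number of social interactions".

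The EMA Questions paragraph of the same section says that surveys consist of "multiple-choice questions (i.e., they do NOT type in answers" and that participants also report "the number of social interactions since the last signal". The response options for the social item are not given. Table 1 of the protocol lists mood and psychotic symptom severity among the secondary EMA outcomes. The sentence stating Hypothesis 2 predicts greater improvement but names adherence, social functioning and service use, not symptom severity.

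**The concern.** One label has to cover an ordered scale, a binary answer and a number of contacts. It is harmless for the binary answer, because a two-category multinomial logit is a binary logit. For a seven-point ordered rating it matters. An unordered logit estimates a separate condition-by-time coefficient for each of six category contrasts. These need not share a sign, and the SAP has no rule for combining them, so the model alone does not say which arm improved more. A cumulative logit gives one signed coefficient.

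Two analysts could both follow the SAP and test different hypotheses on the same ratings, and the choice could be made with the data in view. If treatment moves ratings along the scale in one direction, the unordered joint test also spends degrees of freedom on departures that nobody predicted.

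**Working it through.** **Inputs from the documents.** Seven ordered levels and three prompts a day (protocol section 9). Twelve weeks, so 3 x 7 x 12 = 252, which matches the SAP's maximum. Alpha 0.05, 85 per arm, 20% attrition at 12 weeks, at least 80% power (SAP, Hypothesis 1, Power Analysis). 85 x 0.8 = 68 completers per arm. Two-sided testing is assumed, since the SAP does not state sidedness.

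**The SAP's own power figure.** An endpoint comparison with 68 per arm and a standardised effect of 0.5 gives 83.0%. An effect of 0.4 averaged over weeks 6 and 12, with autoregressive correlation 0.5, 80% retention at week 12 and an assumed 90% at week 6, gives 79.2%. Other readings fall short: 0.4 at a single endpoint with 68 per arm gives 64.5%. The SAP's 80% can therefore be reproduced under some readings; the present point does not turn on which is used.

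**Terms per rating.** Unordered logit: 7 - 1 = 6 condition-by-time terms. Cumulative logit: 1.

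**Power for a common shift.** With the same noncentrality L, power on k degrees of freedom is P(noncentral chi-square(k, L) > 95% point of chi-square(k)). The 95% points are 3.84 (1 df) and 12.59 (6 df).

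| Power on 1 df | L | Power on 6 df |
|---|---|---|
| 80% | (1.960 + 0.842)^2 = 7.85 | 52.1% |
| 90% | (1.960 + 1.282)^2 = 10.51 | 67.0% |

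Regaining 80% on 6 df needs L = 13.62. The ratio is 13.62 / 7.85 = 1.74, or 68 x 1.74 = about 118 persons per arm. The SAP lets condition predict both intercept and growth; if both were tested jointly, 80% on 2 df (L = 9.63) would become 48.6% on 12 df.

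**Simulation, one rating per person.** 85 per arm; common odds ratio exp(0.4 x pi / sqrt(3)) = 2.07. Rank test against 6-df likelihood-ratio test: 76% against 49% with even categories, 71% against 46% with skewed ones. The 6-df test was slightly liberal (about 6% under the null), so its power is if anything flattered.

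**Simulation, clustered ratings.** 68 per arm, 126 answered prompts each, latent person-intercept SD 1.8 and slope SD 1.2, 2,000 runs. A t test on person-level slopes of the score stands in for the ordinal model; Hotelling's T-squared on slopes of six category indicators stands in for the unordered one.

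| Scenario | Ordered | Unordered |
|---|---|---|
| Common shift 0.65, even categories | 77% | 49% |
| Common shift 0.72, skewed categories | 78% | 52% |
| Spread rising 25%, no shift | 4% | 49% |

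The last row is the reverse case: with no common shift, the unordered test does better. All variance components, shift sizes and response rates here are assumptions.

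**The case against.** The strongest reply is that no error is shown. A cumulative logit also has a multinomial sampling distribution, so the SAP wording admits it. The SAP's reference to intercept and growth parameters, rather than to category-specific sets of them, does not favour the unordered reading. This stands: a reader might infer that an unordered fit was planned, and the documents do not establish that. What remains is that the ordinary meaning of the stated model ignores order, and nothing in the text overrides it.

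Four further replies also stand, as limits.

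- The Hypothesis 2 sentence omits symptom severity. The ratings come in through the protocol's secondary-outcome labels and the SAP's listing of EMA outcomes as dependent variables.
- The SAP names no 6-df test, and direction can be read from fitted category probabilities or an expected score by arm. That step would itself need to be specified.
- The drop from 80% to 52% follows from the 80% anchor. At 91% on 1 df the 6-df power is 69%; at 99% it is 92%. Nothing in the documents fixes the anchor.
- The figure of 68 per arm counts completers. EMA dropouts contribute partial data, and the protocol's progress report gives 96% retention to that date.

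Two stronger readings should not be drawn. The SAP infers equal or greater EMA power from the number of observations, and a reader might conclude that EMA power is overstated. The number of prompts is a weak reason in a hierarchical model, but the conclusion is not contradicted. With an effect of 0.4 and 68 per arm, an EMA level contrast has 99%, 91% and 80% power at assumed intraclass correlations of 0.3, 0.5 and 0.7, against 77% for the lab mean of weeks 6 and 12. A growth contrast at intraclass correlation 0.5 falls below a baseline-adjusted lab change only if the SD of true 12-week change exceeds 0.96. A reader might also infer that an EMA comparison with Standard Care, which has no device, is planned. The SAP's EMA model is already restricted to CBT2go against EMA-only.

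**Conclusion.** The point holds as a gap in specification for three secondary symptom ratings. The stated model, read in the usual way, ignores order and yields six condition-by-time terms per rating with no single signed effect. An ordinal form is allowed by the wording but not stated.

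The cost in power, about 28 points (80% to 52%), is conditional on an unordered fit, a joint 6-df test, a common shift and the assumed 80% anchor. It illustrates why the choice matters and does not estimate a loss in this trial. For effects that are not a common shift the ordering can reverse, which is a further reason to settle the choice in advance.

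For social interactions, a number reported through multiple-choice answers is not a contradiction, but without the response options the appropriate model cannot be identified.

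**What to change.** Replace the single EMA sentence in the SAP (Hypothesis 2, Statistical Analysis) with a model for each outcome:

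- **1-7 ratings:** a cumulative-logit mixed model with person-level intercept and slope, one condition-by-time effect (CBT2go against EMA-only, days in study) as the test, and a check of proportional odds.
- **Adherence:** a binary logit with the same person-level terms.
- **Social interactions:** a count model if a number is recorded, or a cumulative logit if categories are recorded. State which, and list the response options.

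The cost is a few sentences and standard model code, with no new data. The drawbacks are that proportional odds has to be checked, and that a one-term ordinal test will miss an effect that changes only the spread of ratings. The SAP's cover letter describes the trial as completed, so if the EMA analysis has already been run, the report should say which logit was used and label the choice post hoc.

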## **8. PROGRESS REPORT**

We are in Year 3 of the 4 year NIMH Award and have recruited and randomized 143 people out of the targeted 255 participants. We have submitted all required data to our sponsor, the NIMH, and have met or exceeded all recruitment targets to date. There are approximately 112 more people to randomize. We have had excellent retention in the trial (96%) and we have had no complaints from participants. We have not reported any data from this trial as the randomization is not locked. The study is listed on Clinical Trials.gov and its actively recruiting.

There have been no Adverse Events in our research study. We have participated in two annual DSMB meetings, the most recent of which was in January 2015. The board voted to approve the study and raised no concerns that required changing any of the protocols, commending the study on its success in recruiting and retention of participants.

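### The SAP extends a continuous-score power claim to hospitalisations/ER visits without a basis; at low event rates power is well below 80%

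*SAP*

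**What the plan says.** SAP, Hypothesis 1, Power Analysis. The sample size is derived for the BPRS total score with a mixed-model method. It uses an autoregressive structure, correlation 0.5 between successive assessments, and 20% attrition at 12 weeks, "assuming an alpha level of 0.05". The claim is at least 80% power for a medium effect "when there are 85 subjects per each condition for a total of 255 subjects". Medium is given no number. The only numeric effect is from the cited meta-analyses, "which revealed a median effect size of 0.4 (small to moderate) in favor of CBT with active comparators".

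SAP, Hypothesis 2. The dependent variables include "PSR Toolkit Composite and Hospitalizations/ER visits". The power paragraph then says that the secondary outcomes have the Hypothesis 1 assumptions and are, for that reason, "independently powered to detect a medium effect size for each measure".

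Protocol, section 9, PSR Toolkit. Hospitalisation and ER data are compiled by staff from medical records under a release of information.

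Neither document gives an event rate, says whether the outcome is binary or a count, names a distribution or link for it, or states a medium effect on its scale.

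**The concern.** For a continuous score, a standardised difference, a correlation structure and a sample size fix the power. For an event outcome they do not. The variance depends on the event rate, and a medium effect means different things as an odds ratio, a risk difference or a rate ratio. The SAP's inference from shared assumptions to equal power therefore does not follow for hospitalisations/ER visits.

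This outcome is named in Hypothesis 2. If it shows no difference, a reader of the SAP would take the result as coming from a comparison with at least 80% power, although no such power was calculated. If events are infrequent, the trial could miss a halving of hospital use more often than it finds one.

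**Working it through.** **Inputs from the documents.** 85 per arm; alpha 0.05; 20% attrition, so 85 × 0.8 = 68 per arm.

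**Assumptions of ours.** Two-sided test, pairwise comparison, medium read as d = 0.5, and all event rates. The Westfall-Young adjustment is left out; it would lower power.

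**1. The plan's own figure.** Simple pairwise comparison of means: power = Φ(d√(n/2) − 1.96). With d = 0.5 and n = 68: Φ(0.5 × 5.831 − 1.96) = 83.0%. The floor of 80% is met for a continuous score. The exact mixed-model calculation cannot be repeated, because the time contrast and the visit-wise attrition are not given.

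**2. Any event versus none, odds-ratio scale.** OR = exp(dπ/√3) = exp(0.5 × 1.8138) = 2.48. The treated rate p₂ follows from the comparator rate p₁ by dividing the odds by 2.48. With p̄ the mean of the two rates, power = Φ{[√n·(p₁ − p₂) − 1.96·√(2p̄(1 − p̄))] / √(p₁(1 − p₁) + p₂(1 − p₂))}.

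Example at p₁ = 20%: odds 0.25/2.48 = 0.101, so p₂ = 9.2%. Power = Φ[(0.893 − 0.978)/0.493] = Φ(−0.17) = 43%.

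| Comparator rate | Treated rate | Power, 68 per arm | Power, 85 per arm |
|---|---|---|---|
| 5% | 2.1% | 15% | 18% |
| 10% | 4.3% | 25% | 30% |
| 20% | 9.2% | 43% | 52% |
| 30% | 14.8% | 57% | 67% |
| 61% (peak) | 38.7% | 74% | 83% |

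With 85 per arm, 80% is reached only at comparator rates of about 47–74%.

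**3. Any event versus none, Cohen's h = 0.5.** h = 2·arcsin√p₁ − 2·arcsin√p₂. With 68 per arm:

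| Comparator rate | Treated rate | Relative reduction | Power |
|---|---|---|---|
| 5% | not attainable | – | – |
| 10% | 0.5% | 95% | 70% |
| 20% | 4.5% | 78% | 79% |
| 30% | 10.5% | 65% | 82% |

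Power reaches 80% from a comparator rate of about 22%. At rates of 30% or less, this reading requires the intervention to remove about two-thirds or more of the events.

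**4. Counts, rate ratio 0.5, 68 per arm.** With comparator mean μ and dispersion k: power = Φ(|ln 0.5|/SE − 1.96), where SE² = (1/μ + 1/(0.5μ) + 2k)/68.

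| μ (events per person) | k = 0 | k = 1 | k = 2 |
|---|---|---|---|
| 0.2 | 31% | 28% | 26% |
| 0.5 | 65% | 52% | 44% |
| 0.72 | 80% | 63% | 52% |
| 1.0 | 91% | 72% | 58% |

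Solving for 80%: 68 × (ln 0.5)²/(1.96 + 0.842)² = 4.16, so μ = 3/(4.16 − 2k). This gives 0.72 for k = 0, 0.95 for k = 0.5 and 1.39 for k = 1.

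**The case against.** A reader might infer from the 74% peak that this outcome cannot reach 80% power at any event rate. The documents do not support that. The ceiling needs a binary endpoint, the logistic conversion of d = 0.5, a two-sided test and 68 per arm, all at once. Each can be disputed:

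- **Effect scale.** Cohen's h = 0.5 reaches 80% at comparator rates of about 22–94%. A standardised risk difference of 0.5 gives about 81.5% wherever it is attainable.
- **Attrition.** The data come from records, so a missed visit need not mean missing hospital data. With 85 per arm the odds-ratio reading peaks at 83%.
- **Endpoint form.** A halved Poisson rate has 91% power at a mean of 1.0.
- **Repeated measures.** The planned model uses several visits. Averaging three visits with autoregressive correlation 0.5 gives a variance factor of (3 + 2 × 1.25)/9 = 0.61 and an effective 68/0.61 ≈ 111 per arm. The odds-ratio reading then reaches 80% at per-visit rates of about 32–84%.

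All of this stands against impossibility. None of it supplies the missing basis: each route needs frequent events or very large reductions, and the SAP assumes neither.

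Two further inferences should be avoided. The progress report says "There have been no Adverse Events in our research study", but nothing shows that admissions were logged as adverse events. Recruitment was also still open with 143 randomised, so this is not a 24-week event rate. And reading medium as 0.4 lowers the odds-ratio peak to 55%, but the BPRS on the same simple pairwise test then has only 64.5%, so that shortfall is not specific to this outcome.

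**Conclusion.** The concern holds in a limited form. The SAP asserts at least 80% power for hospitalisations/ER visits by carrying over assumptions that do not determine the power of an event outcome. Under the odds-ratio reading with 68 per arm, power is 15–57% at assumed comparator rates of 5–30%. As a halved count it is 26–65% at assumed means of 0.2–0.5 events per person with dispersion 0–2. Power of 80% can be reached, but only under conditions that the plan neither states nor justifies.

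The event rates, the value d = 0.5 and the endpoint form are assumptions, because the documents give none. The finding that the claim lacks a basis does not depend on them; the percentages do. This is an unsupported statement about one secondary outcome and leaves the BPRS calculation untouched.

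**What to change.** Limit the power sentence under Hypothesis 2 to the continuous secondary measures. For hospitalisations/ER visits:

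- Drop the 80% claim and give the detectable rate ratio over a stated range of event rates, saying whether 68 or 85 per arm is assumed.
- State the endpoint as a count over 24 weeks, analysed with a log link and a model that allows overdispersion, such as negative binomial. Other count models would also serve; what matters is that the form is stated.
- Say that a null result will be interpreted through its confidence interval and not as evidence of no effect.

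The SAP's cover letter describes the trial as completed, so this is a change to wording and reporting. It needs no new data or participants. The cost is a less favourable stated figure for this outcome.

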**Hypotheses 1 (Primary Outcome):** Compared to EMA and Standard Care, the CBT2go intervention will be associated with greater improvement in global psychopathology (as measured by BPRS Total Score).

**Hypotheses 2 (Secondary Outcomes):** Compared to EMA and Standard Care, the CBT2go intervention will be associated with greater improvement in EMA and standard lab-based measures of medication adherence, social functioning, and hospitalization and emergency service utilization.

**Aim 2 (Moderators and Mediators):** To determine the impact of moderators and mechanisms on outcomes.

**Hypothesis 3 (Cognitive Impairment and Diagnosis):** Neurocognitive ability will account for more variation in device compliance and treatment response than diagnostic group.

**Hypothesis 4 (Awareness and Attitudes):** Improvement in illness awareness and reduction in dysfunctional beliefs will mediate incremental benefit of CBT2go over comparison conditions.

**Exploratory Aim 3:** Explore a predictive model for suicidal ideation in bipolar disorder that includes direct and indirect effects of cognitive performance, inflammatory cytokine levels, and trajectories of negative affect.

**Supplement Aim 1: To evaluate the association between baseline trait and dynamic impulsivity/social threat with lifetime suicide risk and intensity of and intra-individual variability in suicidal ideation**

**Hypothesis 1:** Impaired performance on impulsivity and social threat measures will be associated with higher lifetime rates of suicide attempts, and more severe and more variable suicidal ideation over 24 weeks

**Exploratory:** We will examine these effects by diagnostic group and treatment group assignment

**Supplement Aim 2: Test the accuracy of prediction models with intensive longitudinal data in the two-week window of time before increases in suicidal ideation**

**Hypothesis 2:** Accuracy of our prediction method will be greater than AUC=0.85 in predicting increases and will be greater than that associated with baseline suicide risk

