**Intervention Fidelity:** We will address the relevant components of Treatment Integrity: Competence, Therapist and Participant Adherence, and Treatment Differentiation. Competence will be addressed by requiring the Project Therapist to have at least a Master’s level of training, previous clinical experience with SMI, and attend a full day training on the intervention by Drs [name], [name], and [name]. Therapist Adherence to the manualized protocol will be assessed via audiotapes, supervision, and submitted checklists measuring conformance to session content. Therapist adherence will be monitored by [name] via audiotape for 25% of randomly-selected participants on an ongoing basis. Participant adherence is assessed objectively via device obtained data. Treatment Differentiation is assessed by blinded random selection of 25% of audiotapes 2/year and ratings by [name] the conformance of sessions to condition assigned. Any observed carry-over effects result in ad-hoc retraining in the elements of each of the active conditions. Participants will be asked to sign a separate consent to have these contacts audiotaped. Participants can still participate in the study if they elect not to be audiotaped.

**Intervention Fidelity:** We will address the relevant components of Treatment Integrity: Competence, Therapist and Participant Adherence, and Treatment Differentiation. Competence will be addressed

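### The SAP's rule for Hypothesis 3 does not test Hypothesis 3, and the device-compliance half of the hypothesis has no analysis

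*SAP*

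**What the plan says.** Protocol section 6, Hypothesis 3, states: "Neurocognitive ability will account for more variation in device compliance and treatment response than diagnostic group". The SAP, under Hypotheses 3 and 4, restates this and lists the moderators as "Cognitive ability (MCCB); Diagnosis (BD vs. SZ"). It gives one dependent variable, "Outcome (Slope of change in BPRS between Baseline and Week 24").

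The SAP's decision rule has two parts. First, "Moderation (Diagnosis, MCCB) will be confirmed by the presence of a significant interaction effect (Diagnosis x Condition) on trajectories using GAMMs". Second, "the diagnosis interaction effect will no longer attain significance with cognitive ability entered into the model".

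Device compliance data exist. Protocol section 9, Intervention Fidelity, says "Participant adherence is assessed objectively via device obtained data", and the EMA Questions paragraph says "Participants will respond to surveys three times per day for 12 weeks". The Standard Care paragraph of the same section gives that arm no device. The SAP's power statement for Hypotheses 3 and 4 concerns mediation only.

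**The concern.** H3 is a comparison of two moderators on two outcomes. The rule differs from it in four ways.

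1. It needs diagnosis to appear to moderate, which H3 does not. The clearest way for H3 to be true is that cognition moderates and diagnosis does not, and then the first part should fail.
2. Diagnosis x Condition is the only interaction written out. The SAP does not say whether cognition enters as a main effect or with its own interaction with condition.
3. A p-value moving across 0.05 does not measure which factor explains more variation.
4. Device compliance, half of H3, has no outcome line, model or test.

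As a result, an unconfirmed H3 could mean that cognition does not moderate, or only that diagnosis does not. If MCCB enters with its interaction, a true diagnosis effect can be credited to cognition that is merely correlated with it.

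**Working it through.** The documents give no power or explained-variation figure for H3, so there is no stated figure to reproduce. The check is a comparison of H3 with the rule, then an illustration of how the rule behaves.

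**Inputs from the documents.** 85 per arm, 255 in total, 20% attrition (SAP, Hypothesis 1 power analysis): 85 x 0.8 = 68 per arm and 255 x 0.8 = 204 analysed. The 0.05 level is the one the SAP states for Hypothesis 1; none is given for H3. Surveys: 3 x 7 x 12 = 252 per person. Device arms: 2 x 85 = 170.

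**Assumptions.** Residual SD 1; diagnosis split 50:50; MCCB total SD 1; moderation in CBT2go only. With a 50:50 split, the BD-SZ gap in MCCB equals 2 x the MCCB-diagnosis correlation.

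**Why the first part depends on the gap.** Let bM be the MCCB x CBT2go effect per SD, bD the diagnosis x CBT2go effect, and g the gap. With MCCB left out, the apparent diagnosis interaction is bD + bM x g. If bD = 0 and g = 0 it is zero, and the first part passes at about the size of the test.

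**Illustration 1.** Linear model of a per-person slope, three separate arms, 2-df F tests, 4,000 runs per row. The rule is met if p < 0.05 for Diagnosis x Condition without MCCB and p >= 0.05 once MCCB is added.

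| Truth | Correlation (gap) | Apparent diagnosis interaction | First part passes | Rule met, MCCB main effect | Rule met, MCCB x Condition added | Direct MCCB x Condition test significant |
|---|---|---|---|---|---|---|
| Only MCCB moderates, 0.5 per SD | 0 (0) | 0.5 x 0 = 0 | 6% | 1% | 2% | 84% |
| same | 0.3 (0.6) | 0.5 x 0.6 = 0.3 | 13% | 1% | 11% | 81% |
| same | 0.5 (1.0) | 0.5 x 1.0 = 0.5 | 29% | 2% | 26% | 73% |
| Only diagnosis moderates, 0.8 | 0 (0) | 0.8 | 65% | 1% | 2% | 5% |
| same | 0.3 (0.6) | 0.8 | 66% | 1% | 8% | 5% |
| same | 0.5 (1.0) | 0.8 | 68% | 1% | 17% | 5% |

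A main effect of MCCB common to all arms hardly changes an arm-specific diagnosis difference, so under that reading the rule is almost never met.

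**Illustration 2.** y = 0.4C + bM x M x C + bD x D x C + 0.2M + e, where C marks CBT2go, D is diagnosis and M is MCCB. Gaps of 0, 0.5 and 1 SD; 2,000 trials per cell.

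- Only cognition moderates, 0.4 to 0.5: the first part passes in 6-27%. The rule is met in 2-3% (main effect). With the interaction it is met in 2, 6 and 16% at 0.4, and 2, 7 and 23% at 0.5, as the gap widens. The direct test is significant in 51-84%, but in only 15-19% if the true interaction is 0.2.
- Both moderate, MCCB 0.4 per SD and diagnosis 0.4: rule met in 2-3% or 4-45%.
- Only diagnosis moderates, 0.8: H3 falsely confirmed in about 2-3% or 3-17%.

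**Comparative test.** Percentile 95% bootstrap interval for the unique sum of squares of MCCB x Condition minus that of Diagnosis x Condition; 1,000 trials x 400 resamples. It supports a true H3 in 9-13% (0.4) or 20-25% (0.5), and a false H3 in 0% when only diagnosis moderates. At a 1 SD gap it supports a true H3 less often than the interaction reading of the rule in the same runs: 9 v 17% at 0.4 and 20 v 24% at 0.5.

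**Compliance.** 170 participants, no diagnosis effect, share of surveys answered regressed on arm, diagnosis and MCCB; 600 trials x 400 resamples. At an MCCB-compliance correlation of 0.3, the direct test is significant in 92-98% and the comparative interval lies above zero in 51-64%. At 0.2, the figures are 63-74% and 15-21%.

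**The case against.** **The SAP may imply an MCCB test.** It lists MCCB as a moderator, names it at the head of the rule and cites a moderation framework, so Diagnosis x Condition may be one worked example of two. The rule can also be read as an explaining-away test. That is a fair reading of one gap. It leaves the diagnosis precondition, the missing comparison of variation and the absence of compliance.

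**The assumed effects are large.** The SAP powers the trial on a whole treatment effect of 0.4. With moderation of 0.4 per SD, a person 1 SD below the mean MCCB gains 0.4 - 0.4 = 0; at 0.5 the gain is 0.4 - 0.5 = -0.1. This stands: the contrast between the direct test and the rule is illustrative and shrinks with smaller effects.

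**The comparative test is weak.** At 0.2 its interval lies above zero in only about 1-2% of trials, against about 2-6% for the interaction reading of the rule. This also stands. The case for the comparison is validity: it gave no false support when only diagnosis moderated, and 0-1.5% when the two explained equal variation.

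**Details are open.** The metric, the resampling unit and the handling of penalised smooths need stating, and the GAMM smooths were not simulated. Unique variation credits the overlap between cognition and diagnosis to neither. The 204 uses planned 12-week attrition although the slope runs to week 24, and Protocol section 8 reports 96% retention. These points affect the figures, not the mismatch between rule and hypothesis.

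**Conclusion.** The concern holds, and it rests on the text rather than on the simulation. Followed exactly, the rule cannot confirm H3, except by chance, unless diagnosis also appears to moderate; and H3's compliance half gets no planned answer.

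At a 1 SD gap, with MCCB entered with its interaction, the rule confirms a true H3 (0.4 per SD) in 16% of trials and a false one (diagnosis alone, 0.8) in 17%. In that setting it barely discriminates. All such figures depend on the assumed effects, the 50:50 split and the linear slope model.

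This should be fixed. It bears on the Aim 2 moderator conclusion only.

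**What to change.** 1. Drop the requirement that Diagnosis x Condition be significant first. Fit one model with both MCCB x Condition x Time and Diagnosis x Condition x Time, keeping all three arms, and test the MCCB term directly. That is the moderation test.
2. For the claim that cognition explains more than diagnosis, report the difference in variation (or deviance) uniquely explained by the two blocks, with a 95% bootstrap interval. H3 is supported if the interval lies above 0, contradicted if below, and otherwise inconclusive. Name one metric, the MCCB score and the resampling unit. State that power is low: 9-25% at 0.4 to 0.5 per SD, and about 1-2% at 0.2.
3. Make the same comparison for device compliance, defined as the share of up to 252 surveys answered, in CBT2go and EMA-only.
4. Report the result of the SAP's own rule alongside, saying how MCCB was entered.

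No new data are needed: MCCB, diagnosis, BPRS and device responses are already collected. The cost is SAP wording, one joint model, a compliance model and a bootstrap. The SAP's cover letter says the trial has completed, so the change must be disclosed as a departure from the SAP and labelled post hoc. The drawback is that the comparative claim will often be inconclusive.
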